5.3.3.1. Discontinuation from Treatment

In addition, a subject will be discontinued from the active treatment and continue to be followed if the subject meets any of the following reasons:

- If any of the following criteria for liver-related adverse events are met and confirmed:
 - AST elevation of >5X ULN or greater than or equal to 225 IU/L or
 - ALT elevation of >5X ULN or greater than or equal to 250 IU/L or
 - Total bilirubin elevation >1.5X ULN or
 - Aminotransferase elevation of >3X ULN accompanied by total bilirubin elevation >1.5X ULN
- If any subject experiences any of the following:
 - QTc prolongation as defined by a corrected QT of > 500ms OR > 60ms above baseline measurement
 - Torsades de pointes (torsades, TdP)
 - Unexplained Syncope
 - Seizure in non-epileptic patients
- Medical disease or condition, or any new clinical findings that meet an exclusion criterion or for which continued participation, in the opinion of the site principal investigator or appropriate sub-investigator, would compromise the safety of the subject, would interfere with the subject's successful completion of the study, or would interfere with the evaluation of responses.
- A SAE as defined in the protocol. The subject will be followed until the resolution of the event.

-
- Pregnancy. The subject will be followed up to two months after delivery.
 - New information becomes available that makes further participation unsafe or no longer in the best interest of the subject.
 - Diagnosis of disseminated coccidioidomycosis.
 - Subsequent hospitalization for this CAP episode occurring greater than 72 hours after study randomization.
 - Worsening oxygenation: need for assisted ventilation including continuous positive airway pressure (CPAP), bilevel positive airway pressure (BIPAP), or mechanical ventilation.
 - Unable to adhere to scheduled study visits (e.g. relocation at a distance from the study center that precludes adherence)
 - Determined by a physician's discretion to require additional therapy not indicated in the protocol to ensure his/her health and well-being.

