7.4. Early Termination Visit (if needed)

7.4.1. Before Follow-up Visit 04

The following assessments will be performed at the early termination visit for subjects who withdraw, or are withdrawn or terminated from this study:

- Obtain interim medical/surgical history, including an assessment for new medical conditions and symptoms by interview of subjects and review of the medical record and note any changes since the previous visit.
- Record all concomitant medications on the appropriate data collection form.
- Assess any SAEs and record on SAE form and in AdvantageEDC.
- Complete a targeted physical examination based on symptoms.
- Record vital sign measurements (sitting blood pressure, sitting heart rate, respiratory rate, oral temperature, oxygen saturation and weight).
- Perform urine pregnancy test for women of child-bearing potential.
- Perform a 12-lead ECG if termination occurs before Day 15
- Perform a pill count of study product (fluconazole or placebo) and interview to determine adherence. Following pill count, collect the pill bottle and retain until study product accountability has been completed by the study monitor.
- Complete symptom Assessment including FLEET CAP Score, PROMIS Item Bank v2.0 - Ability to Participate in Social Roles and Activities - Short Form 4a, Extra-Pulmonary Symptom Score and SF-12v2
- Collect the number of days missed from school and/or work due to illness for subjects who were either enrolled in school or employed at baseline.
- Draw venous blood samples for the following:

-
- Safety laboratories (Hepatic function panel (AST, ALT, Alkaline phosphatase and total bilirubin), BUN, Creatinine) [10 mL]
 - Coccidioidal serologies (CF; qualitative IDCF and IDTP; EIA-IgM; EIA IgG; and quantitative IDCF) [15 mL]
 - Quantitative fluconazole level [5 mL]
 - Blood to be banked for future use [15 mL]
 - Contact subject with results of the safety lab testing for follow-up with health care provider if abnormalities are noted.
 - All available coccidioidal serologic results will be made available to the subject. The treatment status will be revealed to the participant. All participants will be invited to remain in study follow-up. Refer subject to their identified health care provider.

7.4.2. After Follow-up Visit 04 A telephone visit will be conducted.

The following assessments will be performed at the early termination visit for subjects who withdraw, or are withdrawn or terminated from this study:

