7.5. Unscheduled Visit

Unscheduled visits are allowed for the following reasons:

- Management of an SAE.
- Performance of additional laboratory tests or procedures for clinically abnormal test values (e.g., confirming elevated levels of liver enzymes).
- Any time the investigator feels that it is clinically appropriate for subject safety.

The following assessments should be made during unscheduled visits:

- Assess the situation which prompted the unscheduled visit
- Perform a targeted physical exam
- Record vital sign measurements (sitting blood pressure, sitting heart rate, respiratory rate, oral temperature, oxygen saturation and weight).

Unscheduled visits will be labeled and documented by the number of the visit the subject just completed, followed by the letter “S” to denote the first unscheduled visit (e.g. 01S, 02S), the letter “T” to denote second unscheduled visit, etc.

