At the screening visit a physical examination will be performed by a clinician licensed to make medical diagnoses. A standard of care physical exam completed by a clinical provider within the 72 hours prior to screening may be used for the screening exam if all appropriate organ systems are examined and documented. The comprehensive physical examination must include the following organ or body system assessments: skin; head, eyes, ears, nose, and throat; thyroid; neurological; chest and lungs; cardiovascular; abdomen (liver and spleen); lymph nodes; musculoskeletal, genitourinary and extremities. Assessments of any specific signs or symptoms reported by the subject must also be performed and documented. Findings from the screening must be characterized as either normal or abnormal, and if abnormal, a description of the abnormality must be provided. Following the screening visit physical examination, targeted physical exams will be performed on Days 22, 29, and 43 if indicated based the subject's interim

medical history, and changes must be classified as new, worsened, or improved from those at screening.

Vital signs (sitting heart rate, sitting blood pressure (mmHg), respiratory rate, oral temperature (°C), oxygen saturation (SpO₂)) and weight will be collected at the screening visit, Days 22, 29, and 43. Vital signs assessed on Day 1 will be considered as baseline. Subjects must not eat anything hot or cold or smoke within 10 minutes prior to taking oral temperature. Height will be collected on Day 1.

A resting 12-lead ECG will be performed at Day 1 or the pre-screening visit and at early termination visits when applicable. An ECG completed as part of standard of care within the past 72 hours and that is available to the study team at the time of screening can serve as the screening ECG and does not require repeating. The ECG will be assessed for QT prolongation as well as other abnormalities indicative of QT prolongation while the subject is on-site for their study-related visit by a clinician licensed to make medical diagnoses.

The FLEET CAP score is an efficacy outcome measure based on a clinical scoring system that allows a constellation of clinical symptoms to be quantified and scored over time: cough, fatigue, chest pain, dyspnea, sputum production, night sweats, fever, and hypoxia. The FLEET CAP score will be completed on Days 1, 22, 29, and 43.

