9.2.2. Serious Adverse Events

Serious Adverse Event (SAE): An adverse event or suspected adverse reaction is considered “serious” if, in the view of either the investigator or sponsor, it results in any of the following outcomes:

- Death
- A life-threatening adverse event*
- Inpatient hospitalization or prolongation of existing hospitalization
- A persistent or significant incapacity or substantial disruption of the ability to conduct normal life functions, or
- A congenital anomaly/birth defect
- Important medical events that may not result in death, be life-threatening, or require hospitalizations may be considered serious when, based upon appropriate medical judgment they may jeopardize the patient or subject and may require medical or surgical intervention to prevent one of the outcomes listed in this definition. Examples of such medical events include allergic bronchospasm requiring intensive treatment in an emergency room or at home, blood dyscrasias or convulsions that do not result in inpatient hospitalization, or the development of drug dependency or drug abuse

*Life-threatening adverse event. An adverse event is considered “life-threatening” if, in the view of either the site principal investigator or sponsor, its occurrence places the patient or subject at immediate risk of death. It does not include an adverse event that, had it occurred in a more severe form, might have caused death.

Death and life-threatening events are part of the efficacy endpoints of this trial and will not be reported or collected as SAEs unless they meet the criteria below.

Only the following events will be considered SAEs:

- Congenital anomalies or birth defect, OR
- Any condition that meets the regulatory definition of a SAE AND is unexpected (per PI) AND is suspected to be directly caused by the study drug (e.g., anaphylaxis, Stevens-Johnson syndrome, exfoliative dermatitis)

Protocol defined SAEs will be:

- Collected from the time of enrollment through visit Day 49
- Assessed for relationship to study product
- Recorded on the appropriate SAE form and eCRF
- Followed through resolution by a licensed study physician listed on the Form FDA 1572 as the site principal investigator or sub-investigator
- Reviewed and evaluated by DMID, the DSMB (periodic review), and the IRB

9.2.3. Procedures to be Followed in the Event of Abnormal Laboratory Test Values or Abnormal Clinical Findings

Study drug will be stopped for the individual subject if:

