- If any of the following criteria for liver-related adverse events are met and confirmed:
 - AST elevation of >5X ULN or greater than or equal to 225 IU/L or
 - ALT elevation of >5X ULN or greater than or equal to 250 IU/L or
 - Total bilirubin elevation >1.5X ULN or
 - Aminotransferase elevation of >3X ULN accompanied by total bilirubin elevation >1.5X ULN
- If any subject experiences any of the following:
 - QTc prolongation as defined by a corrected QT of > 500ms OR > 60ms above baseline measurement
 - Torsades de pointes (torsades, TdP)
 - Unexplained Syncope
 - Seizure in non-epileptic patients

The subject will be referred to an appropriate health care provider for treatment, and will be followed-up until stabilization or resolution.

The abnormal hepatic function testing will be documented on an appropriate eCRF.

Aggregate information regarding abnormalities of hepatic function testing will be presented to the DSMB in their regular meetings.

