9.5. Halting Rules

For all subjects:

- A. If more than 10% (and at least 5) of randomized subjects develop clinically significant elevations in liver enzymes as defined below, study enrollment will be halted for DSMB review.
 - If any of the following criteria for liver-related adverse events are met and confirmed:
 - AST elevation of >5X ULN or greater than or equal to 225 IU/L or
 - ALT elevation of >5X ULN or greater than or equal to 250 IU/L or

-
- Total bilirubin elevation >1.5X ULN or
 - Aminotransferase elevation of >3X ULN accompanied by total bilirubin elevation >1.5X ULN
- B. If more than 1% (and at least 2) of the randomized subjects develop QT prolongation or clinical symptoms indicative of symptomatic QT prolongation as defined below, study enrollment will be halted for DSMB review.
- QTc prolongation > 500ms or >60ms above baseline measurement
 - Torsades de pointes (torsades, TdP)
 - Cardiac Sudden death
 - Unexplained Syncope
 - Seizure in non-epileptic patients

The DSMB will review the study for efficacy according to the interim analysis plan.

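### Halting rule B counts QTc prolongation, but subjects who stay on treatment have no scheduled post-baseline ECG, and the safety-collection rules can leave its clinical events out of the count

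*Combined protocol and SAP*

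**What the plan says.** Rule B in Section 9.5 has five criteria: "QTc prolongation > 500ms or >60ms above baseline measurement", torsades de pointes, cardiac sudden death, unexplained syncope, and seizure in non-epileptic patients. All but sudden death also stop study drug for the individual subject (Sections 5.3.3.1 and 9.2.3). The QTc criterion there reads "QTc prolongation as defined by a corrected QT of > 500ms OR > 60ms above baseline measurement".

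On ECGs, Section 8.1 states: "A resting 12-lead ECG will be performed at Day 1 or the pre-screening visit and at early termination visits when applicable". Section 7.4.1 limits the later one: "Perform a 12-lead ECG if termination occurs before Day 15". Table 12 carries the same limit as a footnote. Visits 02, 03 and 04 (Sections 7.3.1 to 7.3.3) list no ECG. In Section 7.5 the list that opens "The following assessments should be made during unscheduled visits" does not include one either.

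On collection, Section 9.2.1 excludes all non-serious AEs. Section 9.2.2 says that death and life-threatening events "will not be reported or collected as SAEs unless they meet the criteria below". Apart from congenital anomalies, those criteria require the event to be serious, unexpected in the investigator's view, and suspected to be caused by the drug.

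For the liver criteria of rule A, Section 9.2.3 adds: "The abnormal hepatic function testing will be documented on an appropriate eCRF", and "Aggregate information regarding abnormalities of hepatic function testing will be presented to the DSMB in their regular meetings". It has no matching sentence for the QT-related criteria listed beside them.

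**The concern.** A halting rule works only if the events it counts reach the count. Here one criterion needs a measurement that is not scheduled for subjects who stay in the trial. The others depend on events that the collection rules may filter out.

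Section 2.3.1 treats the interaction of fluconazole with macrolides and fluoroquinolones as a real QT risk. It manages that risk with a baseline ECG and exclusions, and rule B is the trial-level check on whether this was enough. The same section says most enrolled subjects will not have coccidioidomycosis, so most of those on fluconazole carry the risk with no fungal infection to treat. If rule-B events are under-counted, enrolment is less likely to be paused for DSMB review when the true rate exceeds 1%.

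**Working it through.** **1. ECGs against the QTc criterion.** A rise above baseline needs a second ECG. Scheduled post-baseline ECGs by visit:

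| Visit | ECG scheduled |
|---|---|
| Day 22, Day 29, Day 43 | none |
| Unscheduled visit (7.5) | not listed, not prohibited |
| Early termination before Day 15 | yes |
| Early termination on or after Day 15 | none |

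A subject who completes treatment therefore has 0 scheduled post-baseline ECGs. QTc prolongation would be found only if an ECG is done for clinical cause or at early withdrawal.

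**2. Clinical events against the collection rules.**
- A syncope that does not meet a serious criterion has no AE form, because non-serious AEs are not collected.
- Torsades is serious, but Section 2.3.1 already links it to fluconazole. An investigator may call it expected, and it then falls outside the protocol's SAE definition.
- A sudden death attributed to pneumonia or to an antibacterial fails the causality condition. It would appear in the mortality outcome (3.2.2, Secondary Outcome 5), with no stated step that assigns it to rule B.
- The final safety analysis (11.4.3) lists examination findings, vital signs, laboratory data and SAEs. It lists neither ECG results nor rule-B events.

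**3. Size (illustration).** The protocol gives no operating characteristics for rule B, so there is no figure to reproduce. Trigger count after n randomised subjects: k(n) = max(2, floor(n/100) + 1), the smallest count that is at least 2 and above 1%. This gives 3 at 250, 6 at 500, 8 at 750 and 11 at 1,000.

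Assumed inputs, none of them in the documents: true pooled rule-B rate p = 2%; share of events that are silent QTc prolongation s, taken as never counted; fraction of clinical events that reach the count c. The counted rate is q = p × (1 − s) × c. The halting chance comes from an exact binomial recursion that stops at the first n where the count reaches k(n).

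| s | c | q | Halt by 1,000, checked after each subject | Halt by 1,000, checked at 250, 500, 750 and 1,000 only |
|---|---|---|---|---|
| 0.50 | 0.5 | 0.02 × 0.50 × 0.5 = 0.50% | 34.3% | 15.5% |
| 0.50 | 1.0 | 0.02 × 0.50 × 1.0 = 1.00% | 82.6% | 66.3% |
| 0.75 | 0.5 | 0.02 × 0.25 × 0.5 = 0.25% | 10.3% | 2.6% |
| 0.75 | 1.0 | 0.02 × 0.25 × 1.0 = 0.50% | 34.3% | 15.5% |

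Counting every event including silent ones (q = 2%) would give 99.9% with checking after each subject.

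Reporting delay matters less than capture. At 1,000 subjects in 60 months (about 0.55 per day), a delay of 22 to 43 days is 12 to 24 subjects. In simulation this lowers the 82.6% to 80.9% and 79.1%.

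**The case against.** The strongest reply has four parts.

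**The data elements are delegated.** Section 9.6.2 says the DSMB charter will define each data element the board needs, and the board may ask for more. Section 11.3.1 says the study will be monitored against the halting rules. The absence of a named report in the protocol may reflect that delegation. This stands, and it limits confidence in the clinical-event gap to moderate. It does not reach the ECG schedule, which the protocol sets out itself.

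**Sites must act on these events.** QTc prolongation, torsades, syncope and seizure each require stopping drug, referral and follow-up. Interim history at Days 22, 29 and 43, the instruction to call about severe reactions, recorded reasons for withdrawal and mortality follow-up are further routes. Section 9.2.1 says relatedness does not decide what is reported and that doubtful cases should be reported. Section 9.2.2 gives convulsions as an example of a serious event. A reader might infer that rule-B clinical events cannot be recorded at all; the documents do not support that. What remains is that none of these routes is tied to the rule-B count, and that the relatedness statement in 9.2.1 conflicts with the causality condition in 9.2.2.

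**Other ways to stop exist.** A reader might infer that enrolment can be paused only through a rule-B count. Section 9.6.2 empowers the Medical Monitor to stop enrolment when halting criteria are reported, but it does not make that the sole route. DMID or the DSMB chair can convene an ad hoc review on immediate concerns, and the DSMB can recommend changes after any review.

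**The ECG schedule is a design choice.** Screening out high-risk patients and relying on for-cause assessment can be defended in a Phase 4 trial of an approved drug with targeted safety collection (9.1). This stands as a reason not to demand scheduled ECGs. It does not justify leaving the QTc criterion in the rule without stating how little it will detect.

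**Conclusion.** The concern holds in limited form. Confidence is high that the QTc criterion will mostly miss asymptomatic prolongation in subjects who stay on treatment, because the schedule contains no ECG that would show it. Confidence is moderate that clinical rule-B events can be lost from the count, because the charter and the Manual of Procedures are not among the documents.

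The second gap is more than missing detail: if the plan is followed exactly, Sections 9.2.1 and 9.2.2 can exclude events that Section 9.5 says to count.

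The actual under-count is unknown. Under the assumed inputs, full instead of half clinical capture adds about 48 percentage points to the halting chance if half of events are silent (82.6 − 34.3 = 48.3), and about 24 if three quarters are silent (34.3 − 10.3 = 24.0). A reader might take the 99.9% full-count figure as the benefit of better recording. It is not attainable that way, since it includes silent events that no form can capture. The change should be made, but nothing here shows that the trial is unsafe as designed.

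**What to change.** 1. Record every rule-B clinical event, and any QTc from an ECG done for any reason, on one eCRF page at Days 22, 29 and 43 and at early termination. Do this in both arms and regardless of expectedness or relatedness. Require entry within 24 hours of site awareness, the limit Section 9.3.1 already sets for SAEs.
2. Under Section 11.3.1, report rule-B counts by arm to the DSMB, with the number of subjects who had any post-baseline ECG.
3. State in Section 9.5 that the QTc criterion relies on for-cause and early-termination ECGs, so a low count does not show absence of a QTc effect.

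The cost is a small data-entry burden at visits that already take an interim history, one DSMB table and some protocol wording. No subject procedure is added.

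Fuller capture also brings more pauses when the true rate is below 1%. At an assumed 0.5% with checking after each subject, going from half to full capture raises the halting chance by 1,000 subjects from 10.3% to 34.3% if no events are silent. If half are silent, it rises from 2.8% (q = 0.005 × 0.5 × 0.5 = 0.125%) to 10.3% (q = 0.25%). A halt pauses enrolment for review and does not end the trial.

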9.6. Safety Oversight (ISM plus SMC or DSMB)

9.6.1. Independent Safety Monitor (ISM)

The ISM is a physician with relevant expertise whose primary responsibility is to provide independent safety monitoring in a timely fashion. For this study an ISM is not required. However, at each site, and at the request of DMID, in real time, the local PI should be able to identify an independent physician to function as ad-hoc ISM. That person should have the privileges to examine the subject, review the subject medical and study record and provide an independent medical assessment and recommendation to DMID.

9.6.2. Data and Safety Monitoring Board (DSMB)

Safety oversight will be conducted by a DSMB that is an independent group of experts that monitors subject safety and advises DMID. The DSMB members will be separate and independent of study personnel participating in this trial and should not have scientific, financial or other conflict of interest related to the study. The DSMB will consist of members with appropriate expertise to contribute to the interpretation of the data from this trial. The membership will include a chairperson and a statistician who are experienced in clinical trials conduct and have prior DSMB experience. The DSMB will review study progress and participant, clinical, safety, and immunogenicity data at the following time points: after 250, 500, and 750 individuals have been enrolled into the trial.

- Data review for enrollment feasibility and safety after 250 individuals are enrolled into the trial (interim review 1).

-
- Data review for enrollment feasibility, safety and futility after 500 and 750 individuals are enrolled into the trial (interim review 2 and 3, respectively).
 - Data review for safety at study specific time frames above; and at least annually.

Ad hoc reviews may be scheduled in response to an anticipated safety issue such as a halting rule being met, or by request of DMID. The DSMB will also have a final review meeting 6 to 8 months after clinical database lock to review the cumulative unblinded safety and efficacy data for the study. For the details of the interim reviews and analyses, consult Section 11.

The DSMB will operate under the rules of a DMID-approved charter that will be written at the organizational meeting of the DSMB. At this time, each data element that the DSMB needs to assess will be clearly defined. Procedures for DSMB reviews/meetings will be defined in the charter. The DSMB will review applicable data to include, but not limited to, study progress and participant, clinical, safety, and immunogenicity data which may include enrollment and demographic information, medical history, concomitant medications, physical assessments, clinical laboratory values, dosing, protocol defined SAEs, and assays results. Additional data may be requested by the DSMB, and interim statistical reports may be generated as deemed necessary and appropriate by DMID. The DSMB may receive data in aggregate and presented by group. The DSMB may also be provided with expected and observed rates of the liver function abnormalities in an unblinded fashion. The DSMB will meet and review this data at scheduled time points or ad hoc as needed during the study as defined in the protocol and DSMB charter. As an outcome of each review/meeting, the DSMB will make a recommendation as to the advisability of proceeding with the study (as applicable), and to continue, modify, or terminate the study.

DMID or the DSMB chair may convene the DSMB on an ad hoc basis according to protocol criteria or if there are immediate concerns regarding observations during the course of the study. The DMID Medical Monitor is empowered to stop enrollment and dosing of the study drug if halting criteria are reported. The DMID Medical Monitor will be responsible for reviewing any protocol defined SAEs in real time. The DSMB will review safety events on a regular basis and ad hoc during the study.

